If the new programme of antenatal care is found to be more effective in preventing neonatal and maternal morbidity, and/or it is found to be less expensive than the traditional programme at the same level of pregnancy outcome, considering that users and providers are more satisfied with the new model, WHO will develop and circulate recommendations for antenatal care to governments and other agencies. It is expected that the new system will allow countries to maximize their resources and concentrate them in the most rational and effective way.

This report describes a descriptive result of a study conducted in Khon Kaen, Thailand.

This is a part of a large multiclinic, multisite, cluster randomized controlled trial. The other 3 sites include Rosario, Argentina, Havana, Cuba and Jeddha, Saudi Arabia. Twelve antenatal care clinics in 12 district hospitals were randomly assigned into 2 groups. Six clinics in the intervention group offered a new model of antenatal care while the other 6 clinics in the control group offered a traditional antenatal care. Recruitment of subjects was from May 1, 1996 to April 30, 1997. Follow up of the recruited subjects was done until October 31, 1997. All the data were entered and updated by the local coordination unit in Khon Kaen and transferred monthly to WHO in Geneva by e-mail. The expected number of subjects from Khon Kaen, Thailand was 6000. The total sample size from 4 sites was about 20000 subjects.

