3.2 Objectives

The objectives of the whole project are :

- To conduct a multicentre, multinational controlled trial comparing two models of antenatal care;
- To establish the relative merits of each model;
- To test whether the proposed new model is more effective than the traditional multivisit model with regard to maternal morbidity and perinatal morbidity and mortality, cost and satisfaction.

The objective of the study at Khon Kaen, Thailand is to participate in the high quality multicentre, multinational randomized controlled trial comparing two models of antenatal care. It was expected to contribute about 6,000 subjects for the whole project.

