As long as this improved care is kept within the framework of traditional care, it should not invalidate comparisons. In fact, it will give the study a stronger arguments in support of the new programme by eliminating the reaction that the new programme is similar to or better than the "old" only because the old was very inefficient. Attempts will be made to demonstrate that the new programme is equal to or better than a "good traditional prenatal care" system.

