proteinuric-preeclampsia or eclampsia (during pregnancy or within 24 h of delivery; post-partum anemia (<90 g/l); severe urinary tract infection/pyelonephritis (requiring antibiotic treatment or hospitalization)

If LNMP not available, use the best "obstetric" estimation; below 10th percentile of international standard

OUTCOMES OF THE ANC RANDOMIZED CONTROLLED TRIAL
(contd.)

C. PROCESS OUTCOMES	Question number in Data Collection Form(s)	Rates
Rate of antenatal hospital admission - total by cause	Hospital admission form	
Rate of elective and emergency cesarean section associated with pregnancy complications (****)	36-46-47 of Summary form	
Days of hospital admission during pregnancy (median)	Hospital admission form	
D. COST OF ANC	Mean (SD) in US\$	
To the health service		
To the patient		
E. SATISFACTION AND PERCEIVED QUALITY OF CARE (only in random sample)		
By the health workers		
By the patient		

**** Excluding intrapartum cesarean section for fetal distress or cephalopelvic disproportion

7. duration of study;
8. loss to follow-up;
9. randomization by cluster;
10. use of randomized pairs or randomized blocks to increase the precision of comparisons;
11. study areas (countries; sites within country; clinics or hospitals within areas).

Changing the specification of any one of the above factors can have a major effect on the estimate of the sample size. Some of these factors have specific relevance in reference to the present protocol.

The major endpoint

Any one of the many endpoints of interest itemized in the protocol can be used to estimate the required size of this study, with the sample size varying by the endpoint chosen. Among these endpoints, there are two primary outcomes of major public health importance which the new programme must demonstrate will not increase: namely, the maternal morbidity index and low birth weight. Thus, the average minimum rate obtained for individual rates from areas to be enrolled in the study (about 10%) will be used to plan the size of the proposed investigation.

Baseline values

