Using the above values and the value for the intra-class correlation coefficient estimated from the Argentinian data set, as well as other values close to it, Formula 2 of Donner's was implemented for a two-sided test, a level of significance of .05 ($z_\alpha = 1.96$) and a power of 80% ($z_\beta = .842$).

The results are shown in Tables 7a, 7b and 7c. Please note that Table 7c presents sample size calculations for $\beta = 0.10$ or a power of 90%. This is done to evaluate the effect on the sample size of an approach to reduce the risk of false negative results. For example, take the usual objective of showing that the new model of ANC is more effective than the traditional model:

		REALITY	
		Equivalent	Not equivalent
DECISION	Equivalent		β
	Not equivalent	α	

β = Probability of concluding that the two methods are equivalent, when in fact they are not (say = 0.10).

Suppose the true O.R. = 1.18; we observe, say OR = 1.10. If SE (LnOR) is 0.05,

$$x^2 = \frac{\text{LnOR}^2}{\text{SE}^2 (\text{LnOR})} = 3.6 < 3.84$$

If we conclude that “methods are equivalent”, we are making a mistake. We will do so whenever we observe $\text{OR} < 1.11$. We want then that the probability of making this mistake to be $\beta < 0.10$. The implications of this requirement on the sample size are presented in Table 7c.

From these tables we can see that for $\alpha = 0.05$ and $\beta = 0.20$ for an OR 1.18 and four study sites, a total sample size of approximately 16,000 women is needed, distributed in ten clinics of 450 pregnancies per study site (Table 7a). If we have five study sites, eight clinics per site will be needed (Table 7b). However, we would like to have a power of 90% ($\beta = 0.10$); we will need twelve clinics of 450 pregnancies in each of the four study sites for a

Table 7(a): Total number of individuals (N) and number of clusters per stratum per group (n), for P_c ranging from .07 to .13 in four strata $\alpha = 0.05; \beta = 0.20$

ρ	OR	Size of temporal block m_1					
		300		450		600	
		N	n	N	n	N	n
0	1.16*	15040	7	15040	5	15040	4
	1.18**	12016	5	12016	4	12016	3
	1.20	9841	5	9841	3	9841	2
.00065	1.16	17963	8	19430	6	20896	5
	1.18	14352	6	15523	5	16695	4
	1.20	11753	5	12713	4	13672	3
.001	1.16	19537	9	21793	6	24049	5
	1.18	15609	7	17411	5	19214	4
	1.20	12783	6	14259	4	15735	4
.002	1.16	24034	10	28546	8	33058	7
	1.18	19202	8	22807	7	26411	6
	1.20	15725	7	18677	6	21630	5

N is value obtained from formula (2) of Donner (1992).

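### The only decision rule in the protocol reads a non-significant difference test as equivalence, although the stated need is to show that low birth weight and maternal morbidity do not increase

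*Protocol*

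**What the plan says.** The protocol describes the purpose of the comparison in four ways that do not agree:

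- Section 3.2 sets superiority: "To test whether the proposed new model is more effective than the traditional multivisit model".
- Section 4.8.1, on the major endpoint, names "two primary outcomes of major public health importance which the new programme must demonstrate will not increase". These are the maternal morbidity index and low birth weight.
- Section 4.5 says "Attempts will be made to demonstrate that the new programme is equal to or better than" a good traditional system.
- Section 1 allows a recommendation if the new programme is more effective, or if it is "less expensive than the traditional programme at the same level of pregnancy outcome".

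The sample size in section 4.8.2 was "implemented for a two-sided test, a level of significance of .05". To explain why 90% power was considered, the section draws a two-by-two table with the decisions Equivalent and Not equivalent, and defines beta as the "Probability of concluding that the two methods are equivalent, when in fact they are not". It then gives an example: "Suppose the true O.R. = 1.18; we observe, say OR = 1.10". With SE(lnOR) = 0.05 the chi-square is 3.6, below 3.84, and the text says that equivalence will be concluded whenever the observed OR is below 1.11.

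Section 4.10.1 asks whether the arms differ on the primary outcomes and names a cluster-adapted Mantel-Haenszel test. Dummy Table V reports a relative risk with a 95% CI for each primary outcome. Neither gives a margin or a threshold for the interval.

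**The concern.** Failing to reject OR = 1 is weak evidence that an outcome has not increased. A real but moderate increase often gives a non-significant result, and the less precise the trial, the more often this happens. The rule in section 4.8.2 therefore rewards imprecision, whereas the requirement in section 4.8.1 puts the burden of proof on the new programme.

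A null result is also a likely one. Section 4.8.1 expects no substantial benefit on perinatal mortality, and section 1 makes a cheaper programme at unchanged outcomes one route to a recommendation. The protocol needs a valid way to establish unchanged outcomes, and the only one it offers cannot do so.

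**Working it through.** **1. The plan's own sample size.** Inputs from section 4.8.2: control rates 0.07, 0.09, 0.11 and 0.13 in four equal strata; OR 1.18, giving 0.0816, 0.1045, 0.1273 and 0.1499; two-sided alpha 0.05; power 90%; clusters of 450; rho = 0.00065 as used in Tables 7a to 7c; 1:1 allocation.

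- n per arm per stratum = (1.96·A + 1.2816·B)² / D², with A = √Σ2p̄(1−p̄) = 0.8749, B = √Σ[p_t(1−p_t) + p_c(1−p_c)] = 0.8746 and D = Σ(p_t − p_c) = 0.06325. This gives n = 2,010, or 8 × 2,010 = 16,080 in all.
- Design effect = 1 + 449 × 0.00065 = 1.29185. Total = 20,773, against 20,780 in Table 7c.
- At 80% power the same steps give 15,518, against 15,523 in Table 7a.

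The sample-size arithmetic is sound for a difference test.

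**2. The protocol's example.** ln(1.10)/0.05 = 1.906, and its square is 3.63, so the test is non-significant. The 95% CI is exp(0.0953 ± 1.96 × 0.05) = 0.997 to 1.213. The result is labelled equivalent, yet the interval includes 1.18. At SE 0.05 the exact cut-off is exp(0.098) = 1.103; the stated 1.11 fits the SE of about 0.053 at 20,780 women.

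**3. How often the rule says equivalent when the outcome has increased.** Twelve clinics of 450 in four sites make 21,600 women, or 2,700 per arm per stratum. SE(lnOR) = √(design effect / Σw), with w = 1/[1/(n·p_c(1−p_c)) + 1/(n·p_t(1−p_t))]. At OR = 1, Σw = 1,350 × 0.358 = 483.3, so SE = √(1.29185/483.3) = 0.0517. At OR 1.10, 1.15 and 1.18 it is 0.0508, 0.0504 and 0.0501.

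P(equivalent) = Φ(1.96 − lnOR/SE) − Φ(−1.96 − lnOR/SE). At rho = 0.002, the highest value tabulated in the protocol, the design effect is 1.898.

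| True OR | 10.0% becomes | rho 0.00065 | rho 0.002 |
|---|---|---|---|
| 1.10 | 10.9% | 53% | 66% |
| 1.15 | 11.3% | 21% | 37% |
| 1.18 | 11.6% | 9% | 22% |

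At rho 0.00065 the rule accepts an observed OR up to exp(1.96 × 0.0517) = 1.107, where the upper 95% limit is about 1.225 (10.0% against about 12.0%).

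**4. An upper-limit rule.** The protocol states no margin, so the margin M is an assumption, shown as a range. With a true OR of 1, power = Φ(ln M/SE − 1.96).

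- M = 1.18, rho 0.00065: at 21,600 women, 0.1655/0.0517 − 1.96 = 1.24, so 89%. At 20,000 women (the total in section 1), SE = 0.0537 and power is 87%.
- Both endpoints, if independent: 0.869² = 0.755 to 0.893² = 0.797.
- M = 1.18, rho 0.002: SE 0.0651 to 0.0627, power 72 to 75% per endpoint.
- 21,600 women, rho 0.00065: 77% for M = 1.15 and 94% for M = 1.20.

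With M = 1.18 and 21,600 women, no increase could be claimed only for an observed OR up to about 1.07, against 1.107 under the present rule. The chance of a false claim at a true OR equal to the margin is 2.5% whatever the precision.

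**The case against.** The strongest reply is that the Equivalent/Not equivalent table only illustrates why more power was wanted ("However, we would like to have a power of 90" per cent). It sits in the sample-size section, it calls the equivalence conclusion a mistake when the true OR is 1.18, and section 4.10.1 does not repeat it. Dummy Table V would show readers the interval. Section 4.8.1 also says, about perinatal mortality, that reliably confirming the absence of a major adverse effect would be prohibitively large and that the study first tests plausibility. All of this stands, and it limits the point. It does not remove it: the illustration still states when equivalence will be concluded, no other criterion appears, and the caution about perinatal mortality does not cover the two primary outcomes, for which section 4.8.1 demands demonstration.

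Three stronger readings are tempting but unsupported:

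- A reader might infer that the chi-square cut-off itself would trigger a WHO recommendation. Section 1 refers to outcome level together with cost and satisfaction, and does not cite that cut-off.
- A reader might infer that the trial was sized to exclude an OR of 1.18. It was sized to detect it with a two-sided difference test. An increase of that size is missed about 9 to 10% of the time under the planning assumptions, which is the beta the protocol openly accepts.
- A reader might infer that the planned size already gives full 90% power for a margin of 1.18. Using the example's SE of 0.05 suggests 91%, but that SE is hypothetical; the plan's own inputs give 87 to 89% per endpoint, and less for both together.

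**Conclusion.** The point holds. The stated aims conflict, and the one rule given cannot support a conclusion that the primary outcomes have not increased. Under the planning assumptions the exposure is mainly to true increases below OR 1.18, and it grows if the intracluster correlation is larger than planned.

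The figures assume a normal approximation on lnOR, control rates of 7 to 13%, clusters of 450 and no losses. The correlation was estimated for low birth weight only, so applying the same figures to the maternal morbidity index assumes the same correlation and a similar rate. The OR of 1.18 is used as a margin for illustration only; the protocol gives it no clinical justification in that role.

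**What to change.** - In section 4.8.2, remove the step from non-significance to equivalence.
- Pre-state a non-inferiority margin that the sponsor justifies. Conclude that there is no increase only if the upper limit of the two-sided 95% cluster-adjusted CI lies below the margin for both the maternal morbidity index and low birth weight.
- Then assess superiority from the same interval.
- Put this criterion in section 4.10.1 on the same effect scale as dummy Table V (the tables plan a relative risk, the sample size uses an odds ratio), and align sections 1, 3.2, 4.5 and 4.8 with it.
- Restate power on this basis, per endpoint and for both, over a range of margins and correlations.

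The cost is wording plus the work of justifying a margin, which must be done before the arms are compared; section 6 says that the comparison had not been attempted. The downside is that no increase becomes harder to claim, and power is modest if the margin is tight or the correlation is high. Reaching 90% per endpoint at a margin of 1.18 would take about 22,145 women at rho 0.00065, close to the planned 21,600, so restating power is preferable to enrolling more.

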4.9 Data Management

A general model for data management is presented here; however, there are some practical considerations at different study sites which have been incorporated locally.

4.9.1 Data Collection

The data collection system of the trial is designed to avoid any additional work for the staff of the clinics. In each participating clinic, one of the staff will be responsible for monitoring medical records and in the intervention clinics, the classifying form.

Mothers will be identified in a record book located at each clinic by subject number, name, address, date of birth, expected date of delivery, subject number and clinic record number starting the first day of the study. To ensure confidentiality, this trial book should be accessible only to responsible officers of the trial. On the trial forms to be completed at the hospital level, names will be omitted and replaced by a subject number, clinic and hospital medical record number, which will be the key identification for each subject in case that additional information is needed at the clinic or hospital level.

Summary data collection ("summary" and "hospital admission" form) will be completed by the "hospital data clerk", who will be responsible for data collection and management at that hospital. This person will complete these forms within 24 hours of delivery.

Basic information will be collected on the content and timing of antenatal care activities in the two arms of the trial (intervention and control). A detailed data collection form describing antenatal care procedures will be added for a random sample of women (10% of total sample) in both groups for a better description of the traditional and new antenatal care programmes, and obtained at the clinic from the medical records. This will be implemented again one year after the initiation of the trial.

Forms will be reviewed again at the hospital with support from the corresponding clinic (if needed) for range errors, logical responses, missing data and overall completeness. Only complete forms will be sent to the data entry and quality control unit located at each study site.

At this unit, following standardized procedures coordinated from Geneva by the Statistics and Data Processing Unit of HRP/WHO, data will be entered and a common error programme will be used for review and cleaning of information. It is expected that only clean data in standard computer format will be sent to the study coordinating centre.

Data collection forms are included in Appendix I.

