4.2 Study Design

A randomized controlled trial is necessary for the evaluation of the effect of antenatal care on pregnancy outcome specifically to control for bias in patient selection, as has occurred in most of the observational studies. Women delivering preterm infants have less "gestational time" for more prenatal visits, thus making the association between prenatal care and prematurity stronger. Conversely, late initiators of prenatal care have fewer preterm newborns because they are still pregnant after 36 weeks, thereby weakening the effect. Women with known medical complications tend to attend early and have more visits but also have more preterm/IUGR infants, producing the U-shaped curve of the association (more care, more preterm/IUGR). Finally, healthy well-educated women who have very low risk for preterm-IUGR will also attend early, have many visits and make the association stronger. All these recognized selection biases, as well as those presently ignored, can only be controlled by a large randomized controlled study design.

The study is a large, multiclinic, multisite, randomized controlled trial of two different models of antenatal care; a new model of care will be compared with the traditional recommended model as it is presently implemented in the selected sites. Maternal, fetal, perinatal, cost and satisfaction end-points will be compared. The trial are conducted in four sites worldwide; each study site will include between ten and twelve antenatal care clinics

[figure not shown]
(clusters). All women attending each clinic will be included in the assessment of the clinic end-points and will be registered on their first antenatal visit and followed until discharge from the hospital post-partum. Deliveries from all ANC clinics (intervention and control) in a particular study site should occur at the selected medical facilities (Figure 1). Antenatal care clinics (cluster randomization), not individual women, will be randomized to the two arms of the study. Randomization will be stratified within each geographic study site by the size of the patient population enrolled in each clinic or cluster (large, medium and small clusters).

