4.8 Sample Size

4.8.1 Background

Sample size estimates depend on a number of practical and statistical considerations, some of which can only be surmised and several of which are somewhat arbitrary. Factors that influence sample size are:

1. major outcome variables of interest;
2. pre-intervention level of the major end-points, and the variability of the endpoints in the absence of intervention;
3. effect of intervention on the endpoints selected for study;
4. the chance of claiming that an effect intervention has occurred, when in fact, no effect was present: the alpha level corresponding to the statistical test of significance;
5. the chance of failing to detect an effect of intervention, when in fact, an effect was present: $\beta = 1 - \text{power of the test of significance}$;
6. participation rates of both individuals and entire clusters;

Table 6 : Outcomes of the ANC Randomized Controlled Trial

A. PRIMARY OUTCOMES	Question number in Data Collection Form(s)	Rate
Rate of maternal morbidity indicator index ⁽⁺⁾	See individual items	> 10%
Rate of LBW (<2500g)	50	> 10%
B. SECONDARY OUTCOMES		
Incidence of proteinuric ^(*) -pre-eclampsia or eclampsia	27	
Prevalence of post partum anemia (hemoglobin <90g/l) ^(**)	38	
Incidence of severe urinary tract infection/pyelonephritis (requiring antibiotic treatment ^(***) or hospitalization)	28 and hospital admission	
Rate of treated syphilis and any other STDs	31	
Rate of post-partum positive syphilis test ^(***) (among women without treatment during pregnancy)	39	
Rate of incomplete tetanus immunization	21	
Rate of post partum hospital stay ≥ 7 days for maternal complications	41-42	
Rate of IUGR ^(#)		
Rate of preterm delivery (<37 weeks)	52	
Rate of spontaneous & PROM pre-term delivery : <35weeks : 35-36 weeks	36	
Rate of medically indicated pre-term delivery : <35 weeks : 35-36 weeks	36-37	
Rate of breech presentation at birth	48	
Rate of very LBW (<1500 g)	50	
Rate of Apgar score <5 at 5'	53	
Rate of I.C.U. stay > 2 days	55 (c)	
Rate of fetal death	49	
Rate of pre-discharge neonatal death	56	

* Proteinuria of 2.0 g or more in 24h or 2+ or more on qualitative examination (dipstick)

** Requires postpartum blood samples

*** Excluding the antibiotics given to treat asymptomatic bacteriuria

+ Maternal morbidity indicator index: the presence of at least one of the following:

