A second workshop was organized for technicians from all 12 district hospitals involved in the trial. Procedures for hemoglobin measurement and VDRL assessment were described and demonstrated by a faculty member from Faculty of Associated Medical Science, Khon Kaen University. All participants practiced the laboratory procedures including hemoglobin determination and VDRL assessment under the supervision of the faculties. This was to ensure the standardization of the laboratory tests included in the study.

A third workshop was specially organized for responsible persons from 6 intervention hospitals. The philosophy of the new antenatal care model was explained to the directors of the 6 hospitals and the personnel responsible for providing antenatal care. The timing and contents of the 4 visits in the new antenatal care model were described in details. A checklist of intervention to be completed in each of the four visits was introduced to ensure a good compliance to a new antenatal care model. This checklist was incorporated into the medical record and is shown in Appendix I. Strong emphasis was clearly made that in this new antenatal care model women are the centre of activities. Adequate time should be allocated for providing relevant health education and allowing pregnant women and their relatives to ask questions.

Contact details of the principal investigators and coinvestigators were provided should they have any uncertainties or questions about the interventions or how to complete forms.

Recruitment started in all 12 district hospitals participated in the study on May 1, 1996 and continued for one year. All women coming for their antenatal care in these 12 hospitals during this one year period were recruited into the study regardless of their gestational age or risk status. Verbally informed consents were obtained only from pregnant women attending their antenatal care in the 6 intervention hospitals. Women who didn't consent for the new antenatal care model were requested to have their antenatal care at the nearby health centers or hospitals. All recruited women were followed up for their pregnancy outcomes. The follow up period extended for another 6 months after recruitment stopped.

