d) Pre-eclampsia admitted to hospital
e) Eclampsia

29. Urinary tract infection

- 1 = No
2 = Yes, no treatment
3 = Yes, with antibiotic treatment
4 = Yes, with hospital admission

30. Vaginal bleeding during pregnancy

- 1 = No 2 = Yes

- a) First trimester
b) Second trimester
c) Third trimester

31. Lowest haemoglobin value during pregnancy g/l

Grid for lowest haemoglobin value

32. Was the mother treated for any of the following conditions during pregnancy?

- 1 = No 2 = Yes

- a) Trichomoniasis, moniliasis or any other abnormal discharge
b) Syphilis
c) Any other sexually transmitted diseases

33. Was external version for breech or malpresentation attempted?

- 1 = No, cephalic presentation
2 = Breech or malpresentation, no version attempted
3 = Version attempted

34. Prelabour rupture of membranes

- 1 = No 2 = Yes

164

Subject number

Grid for subject number

LABOUR AND DELIVERY

35. At admission in labour, did the mother have any of the following conditions?
1 = No
2 = Yes, noted during antenatal period
3 = Yes, first noted at admission

- a) Pregnancy induced hypertension
b) Pre-eclampsia
c) Severe anaemia (< 70 g/l)
d) Chronic hypertension
e) Uterine height low for gestational age
f) Malpresentation or breech
g) Multiple gestation
h) Pyelonephritis or urinary infection
i) Vaginal bleeding
j) Diabetes mellitus
k) Cardiac disease
l) Chronic respiratory conditions
m) Renal disease
n) Pelvic mass
o) Isoimmunization Rh(-)
p) Other

36. Fetal heart rate present at admission in labour
1 = No 2 = Yes

37. Onset of labour
1 = Spontaneous
2 = Induction (Complete Question 38)
3 = Elective caesarean section

38. Indications for induction of labour
1 = No 2 = Yes

- a) Prelabour rupture of membranes
b) Post-term
c) Intrauterine growth retardation
d) Chronic fetal distress
e) Pre-eclampsia
f) Maternal medical complications
g) Pregnancy complications
h) Isoimmunization Rh(-)

POSTPARTUM INFORMATION

39. Lowest haemoglobin value g/l

Grid for haemoglobin value

40. Syphilis test
1 = Negative 2 = Positive

Grid for syphilis test

41. a) Maternal death
1 = No 2 = Yes
b) If Yes, cause of death

Grid for maternal death

ICD-10 code

42. Date of mother's discharge from hospital or death

Grid for date of discharge

NEONATAL OUTCOME

43. Date of delivery or abortion

Grid for date of delivery

44. Time of delivery

Grid for time of delivery

45. Total number of fetuses

Grid for total number of fetuses

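### The 24-hour deadline for the Summary form contradicts follow-up to discharge and the outcomes the form must hold; a lesser point is that the Khon Kaen close falls 12 days short of term for a 12-week booker

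*Protocol*

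**What the plan says.** **Form timing.** Protocol section 4.9.1 makes the hospital data clerk responsible for the Summary and hospital admission forms and adds: "This person will complete these forms within 24 hours of delivery". Section 4.2 says that women "will be registered on their first antenatal visit and followed until discharge from the hospital post-partum".

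Table 6 (printed within section 4.8.1) lists these secondary outcomes:
- "Rate of post partum hospital stay ≥ 7 days for maternal complications"
- "Rate of I.C.U. stay > 2 days"
- "Rate of pre-discharge neonatal death"

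The Summary form in Appendix I asks for "Date of mother's discharge from hospital or death" (item 42), days in intensive or special care (56c), newborn status at discharge (57), day-7 status of newborns referred elsewhere (58) and the newborn's date of discharge or death (59). These are the printed form's numbers; Table 6 cites some items under a number one lower. Dummy Table VII in Appendix III has a row for neonatal deaths at 7 to 27 days.

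**Close of follow-up.** The Executive Summary gives recruitment at Khon Kaen from 1 May 1996 to 30 April 1997 and follow-up to 31 October 1997. The Khon Kaen implementation section (numbered 4.1.6) agrees: "The follow up period extended for another 6 months after recruitment stopped". The timetable in 4.14 ends recruitment in October 1997 and follow-up in April 1998, by month only. Section 4.4.2 aims for a first visit at about 12 weeks and dates delivery at 280 days from the last menstrual period. Section 4.2.5 counts women without an outcome as lost to follow-up.

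**The concern.** A form closed at 24 hours cannot contain a 7-day stay, a 3-day ICU stay or a death on day 4. A clerk who keeps the deadline must leave those items blank or fill them provisionally. A clerk who waits for discharge breaks the deadline. Sites may resolve this differently, and several secondary safety outcomes depend on how they do.

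The fixed close raises a different problem. Among women who book early and are recruited late, those who abort or deliver preterm are observed and those who go to term are not. Whether the outcome is missing then depends on gestational age at delivery, which is itself an outcome and is tied to low birth weight, a primary outcome.

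**Working it through.** **1. Form timing: the requirements side by side**

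| Item | Earliest time it can be final |
|---|---|
| Summary form, section 4.9.1 | 24 hours after delivery (deadline) |
| ICU stay > 2 days (Table 6; item 56c) | after day 2 |
| Postpartum stay ≥ 7 days (Table 6; item 42) | day 7 |
| Pre-discharge neonatal death (Table 6; items 57, 59) | newborn discharge |
| Day-7 status, referred newborns (item 58) | day 7 |
| Deaths at 7-27 days (Table VII) | day 27 |

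No outcome row can be met by the deadline. All but the last can be met by a form completed at discharge, with day 7 for referred newborns. For the last row, item 59 captures a death in hospital. A baby who goes home and dies on day 10 has no route into the data.

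**2. Length of the close at Khon Kaen**

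30 April to 31 October 1997 = 31 + 30 + 31 + 31 + 30 + 31 = 184 days = 26.3 weeks, which reproduces the stated six months.

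From a first visit at 12 weeks (84 days):
- to term: 280 − 84 = 196 days, 12 more than available;
- to 42 weeks: 294 − 84 = 210 days, 26 more than available.

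Recruitment weeks that do not reach 40 weeks by the close = 40 − booking week − 26.3:

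| Booked at (weeks) | Gestation at close, last-day recruit | Last recruitment weeks affected | Share of a 12-month (52.14-week) intake |
|---|---|---|---|
| 6 | 32.3 | 7.7 | 15% |
| 8 | 34.3 | 5.7 | 11% |
| 10 | 36.3 | 3.7 | 7% |
| 12 | 38.3 | 1.7 | 3% |
| 14 | 40.3 | 0 | 0% |

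**3. Share of women affected**

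Inputs from the document: 35.9% booked before 12 weeks (Table 22), or 4.8% in the first trimester (baseline survey, 5.1.3); preterm 8.4% and post-term 7.0% (5.2.5).

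Assumptions not in the document: recruitment uniform over 12 months; early bookers spread evenly from 4, 6 or 8 weeks up to 12; other term births centred on 39.6 weeks; low birth weight in 55% of preterm and 5% of other births.

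Hand check for booking spread over 6 to 12 weeks (mean 9): (40 − 9 − 26.3)/52.14 = 9.0% of early bookers, and 9.0% × 35.9% = 3.2% of all women.

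Simulation:
- With 35.9% early bookers, 2.4% to 3.7% of all women are undelivered at the close. With 4.8%, the figure is about 0.6%.
- With 18 months of recruitment and 35.9% early bookers, it is about 2.0%.
- Among early bookers of the last month (35.9% case), 67% to 82% are undelivered, and 24% to 30% of those captured are preterm.
- Over all women (35.9% case), preterm moves from about 8.2% to 8.4% and low birth weight from 9.1% to 9.2%. With 4.8% early bookers the shifts are below 0.1 point.

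**4. Comparison with missing forms**

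Overall 182/6765 = 2.7% of Summary forms are missing: 70/3449 = 2.0% intervention and 112/3316 = 3.4% control. Banphai, Nongsonghong and Kranuan together miss 5 + 2 + 5 = 12 of 759 + 493 + 859 = 2,111 (0.6%). A strict close would give about 0.024 × 2,111 = 51 at the lower end of the 35.9% case, or 0.006 × 2,111 = 13 in the 4.8% case.

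**The case against.** **On form timing.** Section 4.9.1 should be read whole. Forms are reviewed again at the hospital for missing data, and only complete ones go to data entry. Section 4.9 presents itself as a general model with local adaptation. Khon Kaen sent forms monthly, issued queries and recorded 42 neonatal deaths. This stands as far as it goes. A reader might infer that long stays and later deaths were in fact missed, or were zero by construction. The document does not support that; it shows an instruction that cannot be kept, not a measured undercount. Nor does the late-death row carry an outcome of its own, since Table 6 limits neonatal death to the period before discharge.

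A reader might also infer that the primary maternal index is undercounted, since it includes postpartum haemoglobin below 90 g/l (item 39). The text reviewed here gives no sampling time for that test, so this cannot be shown.

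**On the close.** The 184 days are exact only for Khon Kaen. The month-level timetable in 4.14 allows anything from 152 to 211 days, and section 4.15 says only about six months. The implementation section describes tracing women not delivered two weeks after their expected date, including by home visit. Three large clinics miss far fewer forms than a strict close would produce in the 35.9% case, so strict enforcement is unproven. All of this stands. It limits the size of the point, but the 12-day shortfall against the programme's intended booking week remains.

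It is tempting to read the 2.0% against 3.4% missing forms as truncation that differs by arm. The document gives neither booking age by arm nor reasons for missing forms, so that reading has no support.

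**Conclusion.** The form-timing contradiction holds. The 24-hour deadline, follow-up to discharge, the form's own items and the Table 6 outcomes cannot all be met. If the deadline were followed literally, postpartum stay of 7 days or more, ICU stay above 2 days and neonatal deaths after the first day could not be recorded. Whether any were lost is not shown. The 7-27 day row of Table VII cannot be complete beyond hospital discharge.

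The close of follow-up is a real but small secondary point. It affects early bookers recruited in roughly the last 2 to 8 weeks. The range of 0.6% to 3.7% of women is wide because the document reports two very different early-booking shares, and it rests on the assumptions listed above and on a strictly enforced close. The 24% to 30% preterm figure describes one late-recruited subgroup and should not be read as the effect on the trial. The same close applies to both arms, so it would bias the comparison only if booking gestation differed between them.

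**What to change.** 1. **Form completion.** In section 4.9.1, replace the 24-hour deadline with completion at the later of maternal and newborn discharge, and day 7 for newborns referred elsewhere. The first 24 hours can still be used to open the form. The cost is one sentence and a short delay in sending forms. For data already collected, comparing the date signed on the form with items 42 and 59 would show whether any forms were closed too early.

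2. **Table VII.** Label the 7-27 day row as in-hospital deaths only, or delete it. There is no cost.

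3. **Close of follow-up.** Restrict the analysis set, whatever the outcome, to women whose expected date of delivery plus 2 weeks falls before the cut-off, at least as a sensitivity analysis. The date is on the Subject Number List at registration, including in control clinics, so the rule does not depend on outcome or on a Summary form existing.

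   The cost is a few percent of recruits, somewhat more than the number undelivered, because late recruits who did deliver are dropped too. For booking spread over 6 to 12 weeks, (42 − 9 − 26.3)/52.14 = 12.9% of early bookers. With 35.9% early bookers that is 4.6% of all women, plus about 0.4% from those booking just after 12 weeks, or about 5%. With 4.8% early bookers the total is a little over 1%.

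   The alternative, for any site still open, is to follow to the last expected date plus 2 weeks. If booking can be as early as 6 weeks (an assumption), that is 294 − 42 = 252 days, or 252 − 184 = 68 more, about two months of passive follow-up.
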